STUDY SYNOPSIS

PROTOCOL TITLE:	Sundt™ Carotid Shunt Post Market Clinical Follow-up (PMCF) Study
STUDY DESIGN:	Non-randomized, multi-center, single-arm, all-comers, retrospective Post Market Clinical Follow-up study
PRIMARY OBJECTIVE:	The primary objective of this study is to retrospectively investigate the safety and efficacy of the Integra Sundt™ carotid shunt during endarterectomy procedures.
PRIMARY ENDPOINT:	The primary endpoint of this study is evidence of injury to the artery or cerebral ischemia secondary to shunt placement and removal.
INDICATION:	The Integra Sundt™ carotid shunts are indicated for temporary carotid artery bypass during carotid endarterectomy procedures to help protect the cerebral hemispheres from ischemia during the period of carotid artery occlusion.
STUDY POPULATION:	100 subjects, both male and female, between the ages 18 to 80 in the United States will be recruited for this trial.
INCLUSION CRITERIA:	
Subjects will be included in this study if they meet all of the following inclusion criterion:
 
 1. Between the ages of 18-80 years old 2. Have undergone carotid endarterectomy with any Integra Sundt™ carotid shunt on or before date of study initiation 3. Availability of records on post-operative imaging of the carotid artery either by carotid duplex ultrasound or angiogram
EXCLUSION CRITERIA:	
Subjects will not be included in this study if they meet the following exclusion criterion:
 
 1. Insertion of a carotid shunt at the site of an infection

DESCRIPTION OF SITES:
	
A minimum of 3 sites and a maximum of 10 sites will participate in this study. A maximum of 40 consecutive patients will be enrolled at each site. This study will take place in the United States only.

STUDY DURATION:
	
The study duration from the first patient's chart review to the completion of the last patient's chart review is expected to be 1 year. The study will end when the data for 100 subjects have been collected.


DATA COLLECTION:
	
Retrospective review of patients who underwent carotid endarterectomy will include demographics, procedure details, safety events, and a post-operative assessment.
 
 • Demographics 
 ○ Age ○ Gender ○ Height ○ Weight ○ Relevant Past Medical History 
 • Transient Ischemic Attack (TIA) • Stroke • Asymptomatic Carotid Stenosis • Bleeding Disorder • Diabetes • Smoking • Other relevant past medical history per the investigator's opinion ○ Relevant Past Surgical History 
 • Previous Head or Neck Surgery • Previous Head or Neck Radiation • Previous Vascular Surgery • Other relevant surgical history per the investigator's opinion ○ Diagnosis / Indication for Surgery ○ Relevant Medications • Procedure 
 ○ Date of surgery

	
 ○ Procedure(s) performed ○ Duration of surgery ○ Device information, including lot number ○ Relevant Medications ○ Any complications noted in the operative report and in the investigator’s opinion determined to be related to the device ● Post-operative Assessment (up to 60 days post-procedure) 
 ○ Evidence of cerebral ischemia as indicated by post-operative neurological exam ○ Evidence of injury to artery as seen on post-operative imaging of the carotid either by carotid duplex ultrasound or angiogram

STATISTICAL METHODS & ANALYSES:
	
The post marketing clinical follow up study is a retrospective chart review. All analyses will be descriptive in nature. No formal statistical analyses will be conducted.

1 INTRODUCTION

1.1 Background

Stroke affects nearly 800,000 individuals in the United States per year and is the fifth leading cause of death¹. Carotid artery stenosis—the narrowing of the carotid arteries due to atherosclerotic plaques—is one of the leading causes of stroke. The annual risk of stroke in individuals with asymptomatic carotid stenosis (ACS) is about 1 to 3%, but the risk is around 4 to 12% for individuals with symptomatic stenosis (SCS) without carotid intervention². Early treatment of carotid stenosis (CEA) has the potential to prevent or delay the occurrence of strokes.

Carotid endarterectomy (CEA) is a surgical procedure to remove the stenosis together with unstable plaque, thereby reducing the risk of stroke³. It has been found to be effective in patients with high-grade symptomatic (~70%) or asymptomatic (< 60%) internal carotid artery stenosis and has been proven to be superior to medical management alone⁴. Most perioperative strokes are ischemic in nature, some of which may be caused by the temporary interruption of blood flow during CEA when the carotid artery is clamped³. A carotid shunt may be used to minimize this interruption of blood flow and ensure sufficient cerebral perfusion during carotid cross clamping, which may decrease the incidence of perioperative stroke. Carotid shunting can either be used in all patients undergoing CEA (routine shunting) or in a proportion of patients who are at a high risk of developing cerebral ischemia during carotid clamping (selective shunting). However, there is no conclusive evidence of the superiority of one method over the other, and it often depends on the surgeon's preference and familiarity with the method³⁻⁵.

1.2 Study Device

1.2.1 Device Description

The Integra Sundt™ internal and external (Loop) Carotid Endarterectomy Shunts are designed to provide temporary carotid bypass for cerebral circulation during carotid endarterectomy procedures.

The Sundt™ internal and external Carotid Endarterectomy shunts are constructed of silicone elastomer with stainless steel spring reinforcement to minimize kinking and occlusion of the cannula lumen and to aid in the ease of insertion of the proximal and distal ends. The ends of the shunts have cone-shaped bulbs to facilitate fixation of the shunt in the vessel. Quite frequently in the internal type shunt a distal tourniquet is not required because, if the proper shunt size is selected, the bulb fits firmly enough against the wall of the vessel that there is no bleeding around the distal bulb. A tourniquet is always required on the proximal end of both the external and internal shunts and usually on the distal end of the external shunt

1.3 Intended Use

The carotid endarterectomy shunts are indicated for temporary carotid artery bypass during carotid endarterectomy procedures in order to help protect the cerebral hemispheres from ischemia during the period of carotid artery occlusion. These shunts are designed as temporary indwelling catheters and are not intended for permanent placement.

2 OBJECTIVE AND ENPOINTS

2.1 Primary Objective

The primary objective of this study to retrospectively investigate the safety and efficacy of the Integra Sundt™ carotid shunt during endarterectomy procedures.

2.2 Primary Study Endpoint

The primary endpoint of this study is evidence of injury to the artery or cerebral ischemia secondary to shunt placement and removal.

3 STUDY DESIGN

This is a non-randomized, multi-center, single-arm, all-comers retrospective Post Market Clinical Follow-up study investigating subjects who received a Sundt™ carotid shunt during a carotid endarterectomy before study initiation at the site.

3.1 Study Duration

The study duration from the first patient's chart review to the completion of the last patient's chart review is expected to be 1 year. The study will end when the data for 100 subjects has been collected.

3.2 Study Sample Size

100 patients will be enrolled at up to 10 centers, with up to a maximum of 40 consecutive patients enrolled at each center. Patients will be enrolled at a minimum of 3 centers. This study will take place in the United States only.

4 SUBJECT POPULATION

4.1 Inclusion Criteria

Subjects will be included in this study if they meet all of the following inclusion criteria:

1. Between the ages of 18-80 years old
2. Have undergone carotid endarterectomy with any Integra Sundt™ carotid shunt before the date of study initiation
3. Availability of records on post-operative imaging of the carotid artery either by carotid duplex ultrasound or angiogram

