5 STUDY PROCEDURES

This study is a retrospective review of patients who have undergone a carotid endarterectomy procedure with the use of the Sundt™ carotid shunt prior to study initiation.

Eligible subjects for the study should be identified by the 3-digit site number followed by the 3-digit subject ID. Numbering of the subjects should be done in a reverse chronological order with the most recent subject being 001 followed by the second most recent being 002 and so forth.

Required information will be collected through a review of the patient chart or electronic medical records (EMR) by the Principal Investigator or delegated personnel. The delegated staff

member shall collect demographics, details surrounding the procedure, and the post-operative assessment.

- **Demographics**
 - Age
 - Gender
 - Height
 - Weight
 - Relevant Past Medical History
 - Transient Ischemic Attack (TIA)
 - Stroke
 - Asymptomatic Carotid Stenosis
 - Bleeding Disorder
 - Diabetes
 - Smoking
 - Other relevant past medical history per the investigator's opinion
 - Past Surgical History
 - Previous Head or Neck Surgery
 - Previous Head or Neck Radiation
 - Previous Vascular Surgery
 - Other relevant surgical history per the investigator's opinion
 - Diagnosis / Indication for Surgery
 - Medications
- **Procedure**
 - Date of surgery
 - Procedure(s) performed
 - Duration of surgery
 - Device information, including lot number
 - Medications
 - Any complications noted in the operative report and in the investigator's opinion determined to be related to the device
- **Post-operative Assessment (up to 60 days post-procedure)**
 - Evidence of cerebral ischemia as indicated by post-operative neurological exam
 - Evidence of injury to artery as seen on post-operative imaging of the carotid artery either by carotid duplex ultrasound or angiogram

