5.1 Device Performance

The delegated site staff will collect information regarding the device performance.

The following device performance questions will be part of the case report form and will be collected from the patient medical record including both the operative note and the anesthesia record for the procedure. For the “yes / no” questions below, if the medical record is silent on the answer to the question it will be assumed that the answer is “no”.

1. Was the shunt use routine or selective? If selective, specify the test and the result that led to use of the shunt.
2. Was there any delay in surgery or complication due to preparation of the device for surgery? If yes, please explain.
3. What was the clamping method type for shunt insertion?
4. How long was the carotid artery cross clamped for shunt insertion?
5. Was there any device-related damage to the artery during insertion of the shunt? If yes, please explain.
6. Was there evidence of clot formation within the shunt at any point during the procedure? If yes, describe how this was detected and what was the remedy. What was the impact to the procedure?
7. Was there any evidence of reduced flow within the shunt other than clot formation (e.g. due to kinking, malposition within the artery)?
8. Was there any evidence of excessive bleeding around the shunt after initial placement? If yes, what was the remedy and the result of that remedy?
9. Did removal of the shunt cause vessel injury or complicate closure? If yes, please explain.
10. Was there evidence of post-operative cerebral ischemia noted in the neurological exam?
11. Did the subject experience injury to the artery due to the device as evidenced by the imaging of the carotid artery either by carotid duplex ultrasound or angiogram?
12. Were there any other device-related complications not previously recorded in the case report forms? If yes, please explain.

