7 ETHICS AND REGULATORY REQUIREMENTS

7.1 Confidentiality

In order to observe the confidentiality of personal data, each patient will be allocated a confidential identification code consisting of the investigator site number followed by a 3-digit patient number. CRFs or any other documents submitted to the sponsor will identify the patient by this identification code. Each investigator will maintain a patient identification list which would detail the identification code along with the corresponding patient identifiers (name and date of birth).

Each subject should be numbered in reverse chronological order from 001 as the most recent subject prior to study initiation at the site.

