5. STUDY PROCEDURE

This study is a retrospective review of patients who have undergone a carotid endarterectomy procedure with the use of the Sundt™ carotid shunt prior to study initiation.

Eligible subjects for the study should be identified by the 3-digit site number followed by the 3-digit subject ID. Numbering of the subjects should be done in a reverse chronological order with the most recent subject being 001 followed by the second most recent being 002 and so forth.

Required information will be collected through a review of the patient chart or electronic medical records (EMR) by the Principal Investigator or delegated personnel. The delegated staff member shall collect demographics, details surrounding the procedure, and the post-operative assessment.

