7. STATISTICAL ANALYSES

7.1. General Statistical Considerations

The PMCF is a retrospective chart review. All analyses will be descriptive in nature. No formal statistical analyses will be performed. The study objectives will be presented by summary statistics.

Summary statistics (mean, standard deviation, quintiles, counts, and percentages) will be presented for all demographic (i.e. age, gender, etc.), clinical baseline characteristics (medical history, surgical history, medications), surgical procedures (procedures performed, duration of surgery) and complications.

The primary objective will be evaluated by summarizing the incidence of injury to the artery or cerebral ischemia secondary to shunt placement.

All statistical analysis will be conducted using SAS[®] for Windows, version 9.4 or later.

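### Protocol 5.1 scores a silent chart as no ischemia and no arterial injury, the SAP's missing-data rule points the other way, and neither document names the field behind the primary incidence

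*Protocol*

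**What the plan says.** **Silent records.** Protocol 5.1 lists twelve device-performance questions and states, for those answered yes or no, that "if the medical record is silent on the answer to the question it will be assumed that the answer is" no. Question 10 asks about ischemia noted in the neurological exam. Question 11 asks about device-related arterial injury on duplex ultrasound or angiogram.

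**Entry.** Criterion 2 in Protocol 4.1 is "Have undergone carotid endarterectomy with any Integra Sundt™ carotid shunt before the date of study initiation"; the synopsis has "Have undergone carotid endarterectomy with any Integra Sundt™ carotid shunt on or before date of study initiation". Criterion 3 requires a record of post-operative carotid imaging but puts no date limit on it. Nothing requires a recorded neurological exam.

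**Missing data.** SAP 7.2.7 repeats the twelve questions and omits the silent-record rule. SAP 7.3 plans no imputation and bases all summaries on non-missing data. SAP 7.2.1.2 keeps every shunted endarterectomy patient in the safety population, on which all analysis rests.

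**Primary result.** SAP 7.1 says: "The primary objective will be evaluated by summarizing the incidence of injury to the artery or cerebral ischemia secondary to shunt placement". Protocol 6 says the same. Neither names the variable. The two endpoint components are collected twice: as questions 10 and 11, and as the post-operative assessment items in Protocol 5 and SAP 7.2.6. The latter carry a limit of 60 days and no silent-record rule.

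**Order.** SAP 5 says: "Numbering of the subjects should be done in a reverse chronological order with the most recent subject being 001". Protocol 5 and 7.1 agree. No minimum time between surgery and chart review is set.

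**The concern.** The primary result is one crude incidence, with no test and no threshold, so its meaning depends on who was actually observed. A rule that turns an absent exam into a negative answer merges two kinds of patient: examined and normal, and not known to have been examined. For the intraoperative questions, reading silence as no is a defensible convention, because an operative note would be expected to mention a problem. For question 10 it is weaker, because the silence may mean that no exam was recorded at all.

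Question 11 is less exposed, since criterion 3 guarantees some imaging record. It remains open where the report does not address injury, or where the only image falls outside 60 days and that limit is applied.

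At stake is whether a favourable figure reflects the device or partly reflects undocumented follow-up. Two analysts following different parts of these documents could also report different primary rates from the same charts.

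**Working it through.** **1. The plan's own figure.** The sample size of 100 has no stated rate, precision or power, so there is no derivation to reproduce. The site limits are consistent: 3 × 40 = 120, which is at least 100.

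**2. One patient, three readings.** Take a patient with no neurological exam on record and a clean image.

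| Source of the ischemia component | Rule followed | Result |
|---|---|---|
| Question 10 | Protocol 5.1 | Event-free, in the denominator |
| Question 10 | SAP 7.3 | Missing, out of the denominator |
| Post-operative assessment item | SAP 7.3 (no silent rule there) | Missing, out of the denominator |

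The documents do not choose between the rows.

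**3. Same charts, different rates.** Assume 3 recorded events and *m* of 100 patients unobserved. The silent rule gives 3/100 = 3.0%. The non-missing rule gives 3/(100 − *m*): 3/95 = 3.16%, 3/90 = 3.33%, 3/80 = 3.75%, 3/60 = 5.0%.

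**4. Understatement under the silent rule.** Let *p* be the true rate and *u* the share of events unrecorded and scored no. The expected reported rate is *p*(1 − *u*). The absolute loss is *p* × *u* and the relative loss is *u*. The documents give neither value, so both are assumed.

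| *p* | *u* = 5% | 10% | 20% | 40% |
|---|---|---|---|---|
| 2% | −0.10 | −0.20 | −0.40 | −0.80 |
| 5% | −0.25 | −0.50 | −1.00 | −2.00 |
| 10% | −0.50 | −1.00 | −2.00 | −4.00 |

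(percentage points)

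If only the exam is missing, *u* is the share of patients without an exam times the share of events that are ischemic, provided that missingness is unrelated to outcome. With 10% unexamined and half of the events ischemic, *u* = 0.10 × 0.5 = 5%, and 5.00% becomes 4.75%.

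**5. Why the composite needs two denominators.** Use the same case, per 100 patients, with no overlap of components. The silent rule gives 4.75/100 = 4.75%. Patients with both assessments give 4.5/90 = 5.00%. Keeping every recorded event but dropping other incomplete patients gives 4.75/(90 + 0.25) = 5.26%, because incomplete patients then enter only when they have an event.

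**6. Precision.** The exact 95% interval for 5/100 is 1.6% to 11.3%. With zero events the upper limit is 1 − 0.025^(1/*n*): 3.6% at *n* = 100, 4.0% at 90, 4.5% at 80.

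**7. Time since surgery (secondary).** The number of cases in the 60 days before initiation is volume per month × 60/30.4 × sites. One per month at 3 sites gives 5.9; two per month at 10 sites gives 39.5. If charts are read on the day of initiation, that is 6% to 39% of 100 patients. It halves for reading 30 days later and is zero at 60 days. Volumes and reading dates are assumed, and criterion 3 would remove recent patients not yet imaged. If 20% of patients were read early and 5% to 50% of their events came later, the loss at *p* = 5% would be 5 × 0.20 × 0.05 = 0.05 to 5 × 0.20 × 0.50 = 0.5 points.

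**The case against.** **The SAP may already prevent the harm.** Assuming no from silence is itself a form of imputation, and SAP 7.3 plans none. If the SAP governs, unobserved patients leave the denominator. If the post-operative assessment items feed the endpoint, the silent rule never reaches it. This stands as a limit on the claim: a reader might infer that the primary rate is certain to be biased, and the documents do not establish that. It does not remove the point, because the protocol rule is explicit and nothing says which document or field prevails.

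**Listings give some protection.** SAP 7.2.6 lists post-operative details by subject, and Protocol 10 includes raw data listings. Neither says that an absent exam will be recorded as such, so they help without curing the problem.

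**Direction.** A reader might infer that the whole design pushes the rate down. That holds only for the silent rule. With no minimum time, a recent patient enters only if already imaged. If early imaging is prompted by symptoms (an assumption), that selection could raise the rate.

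**Early chart review matters little.** The endpoint concerns shunt placement and removal, so events plausibly appear early, and 60 days is a ceiling rather than required follow-up. This is fair, and is why timing is secondary here. But Protocol 3.1's statement that the "chart review is expected to be 1 year" covers the study as a whole. It does not say how soon each site reads its charts, so it cannot show that few would be read early.

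**Conclusion.** The point holds as an unresolved conflict between protocol and SAP over the only primary result, with question 10 the main exposure. Under Protocol 5.1 a patient without a recorded exam can count as ischemia-free. Under SAP 7.3 the same patient would be missing. The source of the endpoint is not stated.

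Where the silent rule is applied, the understatement is downward and equals, in relative terms, the share of events unrecorded. At an assumed 5% rate this is 0.25 to 2.0 points for 5% to 40% unrecorded. The larger figure lies within the sampling interval for 5/100, but that does not make it ignorable: it is systematic, and the interval does not reflect it. A reader might infer that the effect is probably small. The documents do not support that, because they give neither the share of charts without an exam nor the reading dates.

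The absence of a minimum time since surgery is a lesser matter. It does not justify moving eligibility back 60 days. This should be corrected, but it does not invalidate the study.

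**What to change.** 1. **Protocol 5.1 and SAP 7.2.7.** Exempt questions 10 and 11 from the silent-record rule. Score no only when a neurological exam (question 10) or an imaging report (question 11) is on record; otherwise code not assessed, treated as missing under SAP 7.3. The rule can stay for the other yes/no questions.
2. **SAP 7.1.** Name the field that feeds the primary summary. Report the number assessed for each component and each component over its own assessed denominator. Show the composite both over all subjects and among subjects with both assessments.
3. **Case report form.** Record the dates of the exam and the imaging, and report how many subjects have each within 60 days.
4. **Secondary, Protocol 5.** Abstract each chart no earlier than 60 days after surgery. This closes the timing gap without changing eligibility or the reverse-chronological numbering. Reconcile criterion 2 between the synopsis (on or before) and Protocol 4.1 (before).

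**Cost.** Text edits and two date fields, with no new visits; the most recent charts wait up to 60 days. The assessed denominator may fall somewhat below 100, with the modest loss of precision shown in step 6 of the working. Enrolment and the imaging criterion stay as they are.

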4.2 Exclusion Criteria

Subjects will not be included in this study if they meet the following exclusion criterion:

1. Insertion of a carotid shunt at the site of an infection

